4.0 Test Schedule

*Treatment should begin \leq 7 working days from registration
 *Variations of +/- 3 days of the scheduled visits are permitted

	\leq21 days prior to registration	Cycle 1 only	For Each of the First Four Cycles				End of Cycle 4	Day 1 Each additional cycle ¹⁷	Day 1 of cycle 9 or at end of treatment	Follow-Up ^{16,18}
			Day 6	Day 1	Day 8	Day 15				
History & Exam, Wt., PS Assessment	X		X ¹²				X	X	X	
Height	X									
CBC w/differential	X		X ¹³	X	X	X		X ¹³		
Chemistry Panel (Na,K,Ca,AST,ALT,Alk Phos,Total Bili, Glucose, Creatinine, Albumin)	X		X	X ¹⁴	X ¹⁴	X ¹⁴	X	X	X	
Serum Creatinine Clearance ¹	X		X				X	X	X	
LDH, Beta-2 Microglobulin, C-Reactive Protein	X						X		X	
Serum TSH ²	X		X					X		
SPEP ³	X		X ¹²				X	X	X	
UPEP (24hr collection) ³	X		X ¹²				X	X	X	
Quantitative Immunoglobulins ³	X		X ¹²				X	X	X	
Serum Free Light Chains ³	X		X ¹²				X	X	X	
Immunofixation-Serum & Urine ⁴	X						X		X	
Bone Marrow Biopsy w/aspirate	X ⁵						X ¹⁵		X ¹⁵	X ¹⁹
Bone Marrow-FISH, cytogenetics	X ⁵									
Metastatic Bone Survey w/ long bones	X ⁵						X		X	
Chest X-Ray	X									

	≤21 days prior to registration	Cycle 1 only	For Each of the First Four Cycles					End of Cycle 4	Day 1 Each additional cycle¹⁷	Day 1 of cycle 9 or at end of treatment	Follow-Up^{16,18}
			Day 6	Day 1	Day 8	Day 15	Day 22				
ECG	X										
Pharmacokinetics ^{6, R}		X ⁶									
INR ⁷			X ⁷	X ⁷	X ⁷	X ⁷	X ⁷	X ⁷	X ⁷	X ⁷	
Pregnancy Testing ⁸	X ⁸		X ⁸						X ⁸	X ⁸	
Education and Counseling Guidance Document ⁹			X ⁹						X ⁹	X ⁹	
Dispense Study Drug ¹⁰			X ¹⁰						X ¹⁰		
Study Drug Compliance (Medication Diary)			X						X	X	
Adverse Event Assessment ¹¹				X	X	X	X ¹⁶	X	X ¹⁶	X ¹⁶	
Survival and Malignancy Surveillance											X ¹⁸

1. Creatinine clearance will be estimated using the Cockcroft-Gault formula. If the patient is >65 y/o and creatinine is <1, use 1 as serum creatinine value to calculate the creatinine clearance, see Appendix IV.
2. To be completed at baseline and then every 3 months.
3. Required at baseline, and then only required if used to assess disease response (see Section 11.2, Table 11.2).
4. Is required at study entry only if not previously performed or test results not available. If complete response is seen a 2nd immunofixation should be performed 4 weeks later to confirm. Urine immunofixation is only required if positive at study entry.

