5. Bone marrow (with aspirate/FISH/cytogenetics) and skeletal survey may be used if performed ≤90 days of study enrollment.
6. Only applies to selected Mayo Clinic subjects registered to the Phase II component. Pharmacokinetics of lenalidomide: 5cc of blood is to be drawn and put into an EDTA tube at the following time points on Day 6 of Cycle 1: 0 (pre-dose), 0.5, 1, 1.5, 2, 3, 4, 6, 8, 24 hr at all dose groups and at 48 and 72 hr for patients in Group B with severe renal impairment or in Group C on dialysis (hemodialysis or peritoneal dialysis). Please see Section 14.2 for processing procedures. Pharmacokinetic samples will be collected from up to 12 Mayo Clinic participants with a minimum of two patients in each group (Groups A, B and C) of the Phase II component.
7. Treatment with Coumadin should be used with caution. If a patient is being treated with Coumadin, close monitoring of INR is required.
8. Pregnancy tests for females of childbearing potential. A female of childbearing potential (FCBP) is a sexually mature female who: 1) has not undergone a hysterectomy or bilateral oophorectomy; or 2) has not been naturally postmenopausal (amenorrhea following cancer

therapy does not rule out childbearing potential) for at least 24 consecutive months (e.g., has had menses at any time in the preceding 24 consecutive months). Pregnancy tests must occur within 10–14 days prior to initiation of Cycle 1 of lenalidomide and again within 24 hours prior to initiation of Cycle 1 of lenalidomide. FCBP with regular or no menstruation must have a pregnancy test weekly for the first 28 days and then every 28 days while on lenalidomide therapy (including breaks in therapy); at discontinuation of lenalidomide and at Day 28 post the last dose of lenalidomide. Females with irregular menstruation must have a pregnancy test weekly for the first 28 days and then every 14 days while on lenalidomide therapy (including breaks in therapy), at discontinuation of lenalidomide and at Day 14 and Day 28 post the last dose of lenalidomide (see Appendix V: Risks of Fetal Exposure, Pregnancy Testing Guidelines and Acceptable Birth Control Methods).

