$$\text{CrCl (mL/min)} = \frac{(140 - \text{age}) \times (\text{weight, kg})}{72 \times (\text{serum creatinine, mg/dL})}$$

Females:

$$\text{CrCl (mL/min)} = \frac{(140 - \text{age}) \times (\text{weight, kg})}{72 \times (\text{serum creatinine, mg/dL})} \times 0.85$$

If the patient is >65 y/o and creatinine is <1, use 1 as serum creatinine value to calculate the creatinine clearance.

7.12 Phase II Component:

- Lenalidomide at assigned dose (as determined by studies in Phase 1 component)
- Dexamethasone 40 mg orally on days 1, 8, 15 and 22
- Anticoagulation (see Section 9.4)

The dose for lenalidomide will be determined for each group in the Phase 1 portion of the study. Each cycle is 28 days. All groups get a 7 day rest (days 22-28) from lenalidomide. Dosing will be in the morning at approximately the same time each day. Only one cycle of study drug will be supplied to the patient each cycle. Lenalidomide capsules should be swallowed whole, and should not be broken, chewed or opened. If a dose of lenalidomide is missed, it should be taken as soon as possible on the same day. If it is missed for the entire day, it should not be made up (this applies to all dosing schedules). For patients in Group C, when a lenalidomide treatment day occurs on a dialysis day, lenalidomide must be taken after dialysis. Patients who take more than the prescribed dose of lenalidomide should be instructed to seek emergency medical care if needed and contact study staff immediately.

Dexamethasone will be given at a fixed dose of 40 mg by mouth once weekly on a 28 day treatment cycle. If a dose of dexamethasone is missed, it is up to the treating physician whether the dose should be made up. In addition, continuing dexamethasone if lenalidomide is stopped is also at the discretion of the treating physician.

Treatment is to be continued as tolerated until disease progression, intolerable toxicity or patient refusal.

7.2 Phase I Dose Escalation and Determination of MTD.

7.21 Dose Escalation of Lenalidomide:

Table 7.211: Group A = Patients with a 30-60 CrCl (mL/min)[□]

Dose Level		Dose	Treatment Day	Rest Day	Route
1*	Lenalidomide	10 mg	1-21	22-28	Orally
2	Lenalidomide	15 mg	1-21	22-28	Orally
3	Lenalidomide	25 mg	1-21	22-28	Orally

Table 7.212: Group B = Patients with CrCl <30 mL/min who are NOT on dialysis[△]

Dose Level		Dose	Treatment Day	Rest Day	Route
1*	Lenalidomide	15 mg	Every other day, days 1-21	22-28	Orally

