2	Lenalidomide	25 mg	Every other day, days 1-21	22-28	Orally
3	Lenalidomide	15 mg	1-21	22-28	Orally
4	Lenalidomide	25 mg	1-21	22-28	Orally

Table 7.213: Group C = Patients with CrCl <30 mL/min who are on dialysis^{#◊}

Dose Level		Dose	Treatment Day	Rest Day	Route
1*†	Lenalidomide	5 mg	1-21 [£]	22-28	Orally
2	Lenalidomide	10 mg	1-21 [£]	22-28	Orally
3	Lenalidomide	15 mg	1-21 [£]	22-28	Orally
4	Lenalidomide	25 mg	1-21 [£]	22-28	Orally

* Starting dose level

Dialysis includes hemodialysis or peritoneal dialysis.

† The starting dose for patients in Group C accrued to dose level 1 cohort (completed September 2010) was lenalidomide 15 mg post dialysis three times weekly on Days 1-21. Starting with protocol version 5.0, if a return to dose level 1 is indicated, lenalidomide 5 mg on Days 1-21 should be used according to the package insert.

£ When a lenalidomide treatment day occurs on a dialysis day, lenalidomide must be taken after dialysis.

□ Group A: As of November 03, 2010, dose level 1 is completed. Dose level 2 is open.

△ Group B: As of November 03, 2010, dose level 1 is completed. Dose level 2 is open.

◊ Group C: As of November 03, 2010, dose level 1 is completed. Dose level 2 is open.

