Time to treatment failure is defined to be the time from registration to the date at which the patient is removed from treatment due to progression, adverse events, or refusal. If the patient is considered to be a major treatment violation or is taken off study as a non-protocol failure, the patient will be censored on the date they are removed from treatment.

Adverse Events: All eligible patients who began treatment will be considered evaluable for assessing adverse event rate(s). The maximum grade for each type of adverse event will be recorded for each patient, and frequency tables will be reviewed to determine patterns. Additionally, the relationship of the adverse event(s) to the study treatment will be taken into consideration. The duration of treatment, dose level and total dose per agent each cycle will also be summarized using descriptive statistics. Lastly, renal function over time will be described using descriptive statistics.

16.38 Pharmacokinetic Analysis:

Pharmacokinetic (PK) analysis will be performed in consented subjects administered a dose during the "Phase II" portion of the trial.

The following pharmacokinetic parameters will be determined using the non-compartmental methods:

- Maximum observed plasma concentration (C_{\max})
- Time to maximum plasma concentration (t_{\max})
- Area under the plasma concentration-time curve from Time 0 to the last measurable time point (AUC)

- Area under the plasma concentration-time curve from Time 0 to infinity (AUC_{∞})
- Apparent total body clearance when dosed orally (CL/F)
- Apparent volume of distribution when dosed orally (V_z/F)
- Terminal elimination half-life in plasma ($t_{1/2,z}$)

The relationship between renal function (CrCl) and PK parameters will be explored.

The results will be summarized by descriptive statistics.

16.4 Data & Safety Monitoring:

Study Monitoring: PrECOG, LLC will be responsible for study monitoring. Refer to Section 19.5 for details.

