# **7. LENALIDOMIDE PHARMACOKINETIC MEASUREMENTS**

The pharmacokinetic sampling will only apply to selected Mayo Clinic patients who are registered in the Phase II portion of this clinical investigation. 5cc of blood will be drawn on Day 6 of Cycle 1: 0 (pre-dose), 0.5, 1, 1.5, 2, 3, 4, 6, 8, 24 hour at all dose groups and at 48 and 72 hour for patients in Group B with severe renal impairment or in Group C on dialysis.

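### On daily regimens the 48 and 72 h PK samples in Groups B and C fall after later doses, so the listed AUC covers a different window in each renal group

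*Protocol*

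**What the plan says.** **Sampling.** Protocol 4.0, footnote 6, sets ten samples (0, 0.5, 1, 1.5, 2, 3, 4, 6, 8 and 24 h) in all groups, with two more "at 48 and 72 hr for patients in Group B with severe renal impairment or in Group C on dialysis". SAP section 7 repeats the scheme, starting "5cc of blood will be drawn on Day 6 of Cycle 1: 0 (pre-dose". The test schedule adds: "Variations of +/- 3 days of the scheduled visits are permitted".

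**Dosing.** Table 7.211 gives Group A lenalidomide on Days 1-21. In Table 7.212, Group B levels 1 and 2 are "Every other day, days 1-21", while levels 3 and 4 are daily on Days 1-21. Under "Table 7.213: Group C = Patients with CrCl <30 mL/min who are on dialysis", all four current levels are daily on Days 1-21, with a footnote: "When a lenalidomide treatment day occurs on a dialysis day, lenalidomide must be taken after dialysis". Protocol 7.12 gives morning dosing at about the same time each day, and the only scheduled lenalidomide rest is Days 22-28.

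**Analysis.** Protocol 16.38 lists "Area under the plasma concentration-time curve from Time 0 to the last measurable time point", plus AUC to infinity, CL/F, Vz/F and terminal half-life. It lists no AUC over a dosing interval. It adds: "The relationship between renal function (CrCl) and PK parameters will be explored". SAP sections 2.1 and 8 leave PK to a separate report.

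**The concern.** An exposure measure used across renal groups should cover the same dosing interval in each. Here the last sample is at 24 h in Group A and at 72 h in Groups B and C. On a daily regimen, further doses are taken between those two times. Taken as written, the listed AUC would be larger in the groups with worse renal function, partly because of when blood is drawn. With up to 12 patients, and as few as two per group, that artefact cannot be separated from a renal effect unless the measure is redefined.

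**Working it through.** **Step 1: calendar.** Take time 0 as the Day 6 dose, with the 24 h sample drawn before the Day 7 dose.

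| Sample | Later doses already taken, daily regimen |
|---|---|
| 24 h | none |
| 48 h | Day 7 |
| 72 h | Days 7 and 8 |

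The visit window does not change this. A start on Days 3 to 9 plus 72 h ends on Days 6 to 12, all inside Days 1-21. This step needs no model. It applies to every current Group C level, and to Group B only if level 3 or 4 becomes its MTD.

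**Step 2: size, as an illustration.** The documents state no PK figure to reproduce. Inputs:
- Half-life 2.8-6.1 h (Protocol 1.3), with 4.0 h added as an assumed midpoint.
- AUC increases of about 140% (moderate) and 240% (severe) from Protocol 1.7, read as multipliers of 2.4 and 3.4. The whole increase is assigned to half-life (assumption).
- One-compartment oral model, ka = 3 per h (assumption), equal doses, daily from Day 1.

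With ke = ln 2 / half-life and dose/V = 1, concentration is the sum over past doses of ka/(ka − ke) × [exp(−ke·x) − exp(−ka·x)], where x is the time since that dose. AUC is the linear trapezoid on the planned sampling times.

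| Base half-life | A half-life | A AUC 0-24 | B half-life | B AUC 0-24 | B AUC 0-72 | B AUC 0-72, later doses withheld |
|---|---|---|---|---|---|---|
| 2.8 h | 6.7 h | 10.49 | 9.5 h | 14.40 | 24.78 | 17.98 |
| 4.0 h | 9.6 h | 14.52 | 13.6 h | 20.12 | 40.48 | 28.65 |
| 6.1 h | 14.6 h | 21.58 | 20.7 h | 30.03 | 69.31 | 50.55 |

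- Within Group B, AUC 0-72 over AUC 0-24: 24.78/14.40 = 1.72, 40.48/20.12 = 2.01, 69.31/30.03 = 2.31. The model's true three-dose ratio is about 3.0. The later peaks are not sampled, so the value represents neither one interval nor three.
- B/A, both on 0-24 h: 14.40/10.49 = 1.37, 20.12/14.52 = 1.39, 30.03/21.58 = 1.39. The inputs imply 3.4/2.4 = 1.42.
- B/A, B on 0-72 h and A on 0-24 h: 24.78/10.49 = 2.36, 40.48/14.52 = 2.79, 69.31/21.58 = 3.21.
- The same with the Day 7 and 8 doses withheld: 17.98/10.49 = 1.71, 28.65/14.52 = 1.97, 50.55/21.58 = 2.34.

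The last line shows that the longer window alone moves the ratio from about 1.4 to 1.7-2.3. The intervening doses take it to 2.4-3.2.

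**Step 3: every-other-day Group B.** Counted from Day 1, doses fall on odd days. Day 6 is then not a dosing day, although time 0 is labelled as the pre-dose sample. The visit window allows Day 5 or 7, but the 72 h sample would still follow the next dose, due at 48 h.

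**The case against.** The strongest reply is that the data already allow a sound analysis. All groups share the same ten samples to 24 h, the SAP leaves PK to a report that is not among these documents, and a PK analyst may well choose a dosing-interval AUC. That stands as a reason for modest weight. But nothing in the documents makes that choice, and the AUC that 16.38 does list gives the wrong comparison.

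Two further points stand. The Group B figures depend on a daily MTD; at levels 1 or 2 the dosing interval is 48 h, so the 48 h sample is an ordinary end-of-interval sample. And a time 0 labelled as pre-dose already implies a dosing day, so the every-other-day mismatch needs only a clarifying phrase.

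On record-keeping, 14.27 asks for sampling date and time but only the date of dosing, and the diaries ask for an amount per day. PK worksheets may exist in the separate study materials, and 14.34 requires the time point with each shipment. So recording dose and dialysis times is a sensible addition, not a proven omission.

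A reader might also infer that half-life and CL/F will be badly wrong. On daily dosing the 24, 48 and 72 h samples are successive troughs, so their log-linear slope in the model is close to zero and would give no usable half-life. But 16.38 does not say that those points enter the terminal fit, nor does it give a CL/F formula, so that error is not prescribed.

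**Conclusion.** The conflict is real for Group C at every current dose level, and for Group B if its MTD is a daily level. The sampling window, in both its length and the doses inside it, is confounded with renal group in the planned CrCl exploration.

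For a daily-dosed Group B, the illustration puts the dose-normalised B/A ratio at 2.4-3.2 instead of about 1.4. These are not estimates. They rest on a one-compartment model, an assumed absorption rate, and the whole rise in exposure placed in half-life. The cited moderate group is CrCl 30-50 mL/min, whereas Group A is 30-60. No reliable figure can be given for Group C: the cited exposure is off dialysis, and dialysis clearance and dose timing would have to be modelled.

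It would go too far to infer that the trial's main conclusions are at risk. PK is a descriptive secondary objective (2.24) in up to 12 patients; the MTD and response analyses do not use it.

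**What to change.** In 16.38, or in the plan for the separate PK report before concentrations are analysed:

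1. Replace AUC to the last sample, as the between-group exposure measure, with dose-normalised AUC over the actual dosing interval. On daily regimens this is 0-24 h, from samples that all groups already have.
2. Exclude samples drawn after a later dose from AUC and terminal half-life. Use them only as trough checks.
3. Record dose clock times with each profile and, for Group C, dialysis times.

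The sponsor should reconcile footnote 6 and SAP section 7 with Tables 7.212 and 7.213 on two matters: whether doses continue during the 72 h of sampling, and which day the profile is taken under every-other-day dosing. No dosing rule is proposed here.

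The cost is wording and a few recorded times, with no extra blood draws. The downside is that half-life, AUC to infinity and Vz/F stay imprecise in Groups B and C on daily dosing. Group C intervals may also differ from 24 h, because lenalidomide follows dialysis on dialysis days, so that AUC has to be read with the dialysis times.

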5.0 Stratification Factors

- 5.1 Renal Impairment: Group A: Moderate renal dysfunction (CrCl 30-60 mL/min) vs. Group B: Severe renal dysfunction (CrCl <30 mL/min, not requiring dialysis) vs. Group C: ESRD renal dysfunction (CrCl <30 mL/min, requiring hemodialysis or peritoneal dialysis)
- 5.2 Component: Phase I vs. Phase II
- 5.3 Dose Level: 1 vs. 2 vs. 3 vs. 4

6.0 Registration/Randomization Procedures

6.1 Ethics

This study will be conducted in accordance with the ethical principles that have their origin in the current Declaration of Helsinki and will be consistent with applicable US regulatory requirements and International Conference on Harmonization Good Clinical Practice (ICH GCP).

The study will be conducted in compliance with the protocol. The protocol and any Amendments and the patient informed consent will receive Institutional Review Board (IRB) approval prior to initiation of the study.

Freely given written informed consent must be obtained from every patient or their legally acceptable representative prior to clinical trial participation, including informed consent for any screening procedures conducted to establish patient eligibility for the trial.

Study personnel involved in conducting this trial will be qualified by education, training, and experience to perform their respective task(s). This trial will not use the services of investigators or study personnel where sanctions have been invoked or where there has been scientific misconduct or fraud (e.g., loss of medical licensure, debarment). Investigators are responsible for the conduct of the study at their study site.

6.2 Regulatory Requirements

Before a site may enter patients, protocol-specific regulatory and other documents must be submitted to PrECOG representatives as noted in study materials. Detailed information regarding document submission and control is provided to each site in separate study materials.

Once all required documents are received, reviewed, and approved by PrECOG or their representative, a registration information packet will be forwarded to the site. Any changes to site regulatory documents must be submitted by the investigator to the responsible party in a timely manner. Initial study drug shipment will not occur until the regulatory packet is complete. No patients should begin protocol therapy without formal registration as per the process below.

6.3 Registration Procedures

6.31 Phase I Dose Escalation – Prior to discussing protocol entry with patient **AND** prior to registering a patient through the electronic data capture (eDC) system, call the PrECOG Project Manager to ensure that a place on the protocol is open to the patient. The Project Manager contact details can be found in the Study Reference Manual.

6.311 Patients must not start protocol treatment prior to registration.

Patients must meet all of the eligibility requirements listed in Section 3.0 prior to registration. Treatment should begin ≤ 7 working days from registration.

An eligibility checklist is included in Appendix XI and a usable version is available in separate study materials provided to the site. A confirmation of eligibility assessment by the investigator and/or site will be performed during the registration process.

Upon determination that a subject meets eligibility criteria, the subject will be registered in the study by site personnel via an electronic data capture eDC system. Confirmation of registration will be displayed in the eDC system once site personnel have verified the subject's eligibility status.

Full information regarding registration procedures and guidelines can be found in the Study Reference Manual provided to your site. All correspondence regarding patient registration must be kept in the study records.

6.32 Phase II Patient Registration

Patients must not start protocol treatment prior to registration.

Patients must meet all of the eligibility requirements listed in Section 3.0 prior to registration. Treatment should begin ≤ 7 working days from registration.

An eligibility checklist is included in Appendix XI and a usable version is available in separate study materials provided to the site. A confirmation of eligibility assessment by the investigator/site will be performed during the registration process.

Upon determination that a subject meets eligibility criteria, the subject will be registered in the study by site personnel via an electronic data capture (eDC) system. Confirmation of registration will be displayed in the eDC system once site personnel have verified the subject's eligibility status.

Full information regarding registration procedures and guidelines can be found in the Study Reference Manual provided to your site. All correspondence regarding patient registration must be kept in the study records.

6.321 Body Fluid Biospecimens

A mandatory translational research component for blood specimens is part of this study; the patient will be automatically registered onto this component (Sections 3.18c, 4.0 and 14.0). Only applies to select Mayo Clinic subjects registered to the Phase II component.

- 6.4 Pretreatment tests must be completed within the guidelines specified on the test schedule.
- 6.5 All required baseline symptoms must be documented and graded.
- 6.6 Study drug availability checked.

